## **2. STUDY OBJECTIVES AND ENDPOINTS**

### **2.1. Objectives**

To determine the safety and tolerability of multiple doses of PF-06741086 administered to severe hemophilia A and B subjects with and without inhibitors against FVIII and FIX.

#### **2.1.1. Key Secondary Objective**

- To assess the clinical efficacy of repeat dosing of PF-06741086.

#### **2.1.2. Secondary Objectives**

- To characterize the PK profile of PF-06741086.
- To characterize the PD profile of PF-06741086.
- To characterize the immunogenicity of PF-06741086.

CCI

## 2.2. Endpoints

### 2.2.1. Primary Endpoints - Safety

- Frequency, severity and causal relationship of treatment emergent adverse events (AEs) (treatment emergent adverse events [TEAEs]) and withdrawals due to TEAEs; Day 1 up to Day 113.
- Frequency and magnitude of abnormal laboratory findings (including hematology, PT/INR, aPTT, chemistry, urinalysis, fibrinogen, ATIII activity and cardiac troponin I); Day 1 up to Day 113.
- Changes from baseline in vital sign (blood pressure, pulse rate, temperature and respiration rate) measurements 12-lead electrocardiogram (ECG) parameters and physical examination; Day 1 up to Day 113.
- Frequency, severity and causal relationship of infusion and injection site reactions; Day 1 up to Day 113.

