### 1.3.2. Study Rationale

The clinical investigation of PF-06741086 will continue with study B7841002, an open-label, Phase 1b/2, multiple ascending dose (MAD) study in severe hemophilia A or B subjects, including subjects with inhibitors to factor VIII or factor IX. The clinical risk/benefit profile for this population is considered appropriate for the evaluation of safety, tolerability, PK, PD, and efficacy of multiple doses of PF-06741086. Frequency of bleeding episodes (of study subjects during treatment with PF-06741086) will be compared against the frequency of bleeding episodes in an external control group as a measure of therapeutic efficacy.

The primary objective of study B7841002 is to evaluate the safety and tolerability of multiple ascending doses of PF-06741086 administered by the SC or IV route. Secondary objectives include evaluating the PK and PD properties of PF-06741086, as well as assessing clinical efficacy based on the frequency of bleeding episodes. Selection of the PD endpoints and sampling schedule are based on results from non-clinical studies and the Phase 1 FIH study results. They will reflect either target binding by PF-06741086 (ie, TFPI level) or downstream pharmacologic effects of TFPI inhibition (ie, dPT, TGA, PF1+2 and D-dimer). Thrombosis is a potential risk for inhibition of TFPI, and PF-06741086 is expected to significantly inhibit TFPI, particularly at the highest dose levels. To minimize this risk, hemophilia patients with a known history of thrombotic, ischemic or coronary artery disease, or known pro-thrombotic conditions (eg, Protein C deficiency) will be excluded from this study. Safety monitoring will include laboratory parameters that may be modulated due to coagulopathy (eg, [PT]/INR, aPTT, fibrinogen, ATIII and platelet counts) and parameters to screen for possible thrombotic events (eg, cardiac troponin I). Laboratory endpoints to detect excessive modulation of the coagulation pathway will be monitored during the period of peak drug exposure, until at least 28 days have passed since the final administration.

Potential risks for treatment with PF-06741086 are thrombi or emboli. Depending on location and severity, thrombi or emboli may be life threatening or fatal. An additional potential risk for treatment with PF-06741086 is ADA-induced hypersensitivity.

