### **Dose Modifications**

Any subject who experiences a dose limiting toxicity (per [Appendix 2](#)) will be discontinued from treatment with the investigational product and will be followed for adverse event monitoring until resolution of the respective toxicity and elimination of study drug or the end of the study (Day 113) and resolution or stabilization of the respective toxicity, whichever occurs first. In addition, subjects who have not experienced dose limiting toxicities but are currently receiving a dose that met the dose limiting toxicities criteria for termination of dose escalation as defined in [Section 3.3](#) will be removed from the current dose level and dropped to the next lowest exposure level.

Subjects who have not experienced a dose-limiting toxicity may also require dose modifications. Criteria for modifications of dosing in an individual subject are as follows:

- Moderate severity infusion/injection site reactions at more than 2 consecutive visits (eg, Day 22, Day 29, and Day 36);
- Treatment emergent adverse event(s) that increases in severity/grade, without resolution, (eg, Mild to Moderate and continuing) after repeat administration of PF-06741086;

- Treatment emergent adverse event(s) of any severity with more than 2 occurrences following repeat administration of PF-06741086.

Any subject who meets the above criteria during treatment with PF-06741086 will be removed from the current dose level and dropped to the next lowest exposure level, unless the event(s) are incontrovertibly due to extraneous causes or are incontrovertibly complications of hemophilia (see [Section 8.6](#) for qualifying events).

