## 7.1. Safety

### 7.1.1. Laboratory Tests

The following safety laboratory tests will be performed at times defined in the **STUDY PROCEDURES** section of this protocol. Additional laboratory results may be reported on these samples as a result of the method of analysis or the type of analyzer used by the clinical laboratory; or as derived from calculated values. These additional tests would not require additional collection of blood. Unscheduled clinical labs may be obtained at any time during the study to assess any perceived safety concerns.

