### 7.7. Blood Volume

The total blood sampling volume for individual subjects in this study is approximately 389.3 mL for SC cohorts and 428.7 mL for IV cohorts (based on Screening through Day 113). The table below reflects approximate sample volumes needed for each measured endpoint. The actual collection times of blood sampling may change, but the total blood volume collected should not increase. Additional blood samples may be taken for safety assessments at times specified by Pfizer, provided the total volume taken during the study does not exceed 550 mL during any period of 30 consecutive days.

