**Table 6. Blood Volume for SC Cohorts**

Sample Type	Sample Volume (mL)	Number of Sampling Times			Total Volume (mL)
		Screening	Study Period	Follow-Up	
Safety Labs					157
Serum chemistry (with Lipid profile a )	5	1	7	1	45
Hematology	3	1	7	1	27
Prothrombin 20210 mutation	3	1	0	0	3
Factor V Leiden mutation testing	3.5	1	0	0	3.5
aPTT, PT/INR, Anti-thrombin III b , Factor VIII and Factor IX activity c , Fibrinogen, Protein C a , Protein S a , D-dimer, PF1+2 (PD samples) [Single combined sample]	4.5	1	11	1	58.5
Serology (HBs Ag, HBc Ab, HCV Ab, and HIV)	5	1	0	0	5
Cardiac Troponin I d	3	0	5	0	15
PK	4.5	0	11	1	54
Immunogenicity (ADA, NAb)	9	0	5	1	54
PD (note some PD assayed from safety samples)					106.8
TFPI level	2.7	0	11	1	32.4
TGA	3.5	0	11	1	42
dPT	2.7	0	11	1	32.4
Factor VIII and Factor IX inhibitor a	4.5	1	0	0	4.5
CCI [REDACTED]	[REDACTED]	[REDACTED]	[REDACTED]	[REDACTED]	[REDACTED]
Banked biospecimens	4	0	1	0	4
TOTAL					393.8

a at Screening only.

b at Screening and Days 1, 8, 15, 22 and 29 only.

c at Screening and Day 1 only.

d at Days 1, 8, 15, 22 and 29 only.

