6.5.4. Electrocardiogram

Absolute values and changes from baseline in QT, heart rate, QTcF, PR, RR and QRS will be summarized by dose level and cohort and study day using sponsor reporting standards. Tables will be paged by parameter. Baseline is as defined in [Section 3.1.4](#).

The maximum absolute value (post-dose) and the maximum increase from baseline for QT, heart rate, QTcF, PR, and QRS will be determined over all measurements taken post-dose.

The maximum increase from baseline will be calculated by first subtracting the baseline value from each post-dose measurement to give the change from baseline. The maximum of these values over the respective period will then be selected, except in the case where a subject does not show an increase. In such an instance, the minimum decrease should be taken.

Maximum increase from baseline for QT, heart rate, QTcF, PR and QRS will be summarized by dose cohort, according to sponsor reporting standards.

ECG endpoints and changes from baseline (QTcF, PR and QRS) will also be summarized descriptively by dose level and cohort and study day using categories as defined in [Appendix 1](#) (for QTc these correspond to ICH E14).¹ Numbers and percentages of subjects meeting the categorical criteria will be provided. All planned and unplanned measurements will be counted in these categorical summaries. All values meeting the criteria of potential clinical concern will be listed.

Listings of subjects with any single postdose value ≥ 500 msec will also be produced for QTcF.

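### ATIII, cardiac troponin I and ECG are primary safety endpoints to Day 113, but none is scheduled after the pre-dose Day 29 visit

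*Protocol*

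**What the plan says.** **Endpoint window.** Protocol 2.2.1 puts ATIII and troponin among the abnormal laboratory findings: "fibrinogen, ATIII activity and cardiac troponin I); Day 1 up to Day 113". The next bullet covers "12-lead electrocardiogram (ECG) parameters and physical examination; Day 1 up to Day 113". SAP 3.1 repeats both.

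**Schedule.** Table 1 has all three at Days 1, 8, 15, 22 and 29. Table 2 (Day 30 to Day 113) has no row for any of them, although it keeps PT/INR, aPTT and fibrinogen at Days 57, 85 and 113. The visit lists in 6.2.4, 6.2.6, 6.2.8 and 6.3.1 and the early-withdrawal list in 6.4 omit them as well. In Tables 6 and 7, footnote d limits troponin to samples "at Days 1, 8, 15, 22 and 29 only", and footnote b limits ATIII to Screening and the same days.

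**Related statements.** Section 1.3.2 names ATIII as a coagulopathy parameter and troponin as a screen for thrombotic events. It then commits to laboratory monitoring for excessive coagulation modulation "until at least 28 days have passed since the final administration". Appendix 2 makes troponin and ECG values dose-limiting toxicities, and Section 3.3 (Dose Modifications) says an affected subject "will be discontinued from treatment with the investigational product". SAP 6.5.4 states that ECG maxima "will be determined over all measurements taken post-dose".

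**The concern.** The primary objective is the safety of multiple doses, and dosing continues to Day 78 (SC) or Day 57 (IV). If the three measures stop before the Day 29 dose, the stated endpoint describes a period that the trial does not measure on schedule.

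Three things follow.

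- **Repeat dosing.** IV repeat doses have no scheduled follow-up on these measures. This is the regimen with the highest predicted peak: 313,000 ng/mL at steady state (Table 4), against a geometric mean of 152,800 ng/mL at the highest dose in the first-in-human study (Table 3).
- **Stopping criteria.** After Day 29 the troponin and ECG toxicity criteria can be met only through an unscheduled test, while subjects are still being dosed.
- **Selective data.** Section 7.1.1 says: "Unscheduled clinical labs may be obtained at any time during the study to assess any perceived safety concerns". Later values would therefore come mainly from subjects who already gave cause for worry, with no proper denominator for a frequency endpoint. SAP 6.5.4 counts unplanned ECGs in its categorical tables, so such values would be mixed with scheduled ones.

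**Working it through.** No power or sample-size formula applies. The check counts nominal visits and doses, ignoring visit windows.

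**Reproducing the plan's own figure.** Tables 6 and 7 show 5 study-period troponin samples and 0 at follow-up. Days 1, 8, 15, 22 and 29 give 5 × 3 mL = 15 mL, as printed.

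**Is the Day 29 test pre-dose?** Section 6.2.3 lists the ECG and blood samples, then dosing once pre-dose procedures are complete. It also has an IV post-infusion draw on Day 29 without naming the tests. That draw does not supply the missing results:

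- Troponin: Table 7 counts five samples for five named days, so there is no second Day 29 sample.
- ATIII: the IV cohort has 12 combined coagulation tubes against 11 for SC. The one extra matches the Day 1 post-infusion D-dimer and PF1+2 draw in 6.2.1.

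**Coverage of the window.**

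- Window: 113 − 1 = 112 days.
- After the last scheduled test: 113 − 29 = 84 days, and 84/112 = 75%.

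**Doses with no later scheduled result.**

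| Route | Dose days | Before the Day 29 tests | After them |
|---|---|---|---|
| SC weekly | 1, 8, 15, 22, 29, 36, 43, 50, 57, 64, 71, 78 | 4 | 8 of 12 |
| IV monthly | 1, 29, 57 | 1 | 2 of 3 |

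Each subject has 4 scheduled post-dose results (Days 8, 15, 22 and 29). In SC cohorts they follow doses 1 to 4. In the IV cohort all 4 follow dose 1.

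**Section 1.3.2 commitment, applied to ATIII.**

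- SC: 78 + 28 = Day 106; ATIII stops 106 − 29 = 77 days short.
- IV: 57 + 28 = Day 85; ATIII stops 85 − 29 = 56 days short.

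**Can the existing blood draws carry the fix?** The combined 4.5 mL tube holds ATIII with PT/INR, aPTT, fibrinogen, D-dimer and PF1+2. The 11 SC study-period draws are Days 1, 2, 4, 8, 15, 22, 29, 30, 33, 57 and 85, with one more at follow-up (Day 113). The tube is therefore already taken at Days 57, 85 and 113, and ATIII needs no extra blood.

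Troponin at those three visits adds 3 × 3 mL = 9 mL:

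- SC: 393.8 + 9 = 402.8 mL (9/393.8 = 2.3%).
- IV: 433.2 + 9 = 442.2 mL (9/433.2 = 2.1%).

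Both whole-study totals are below the 550 mL that Section 7.7 allows in any 30 days. These are the table totals; the prose of 7.7 gives 389.3 and 428.7 mL, each 4.5 mL lower.

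**The case against.** The schedule itself is not in dispute. The case on the other side concerns its importance.

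- **The 75% looks worse than the loss.** Even the fully covered tests (PT/INR, aPTT, fibrinogen) have only three visits after Day 29, so the shortfall is 3 of 7 post-dose visits. Of the 84 days, 113 − 78 = 35 (SC) or 113 − 57 = 56 (IV) follow the final dose. This is fair context; the count is still correct.
- **Exposure is largely covered.** The protocol treats Day 29 to 36 as its multiple-dose interval for SC. For IV, the predicted trough of 8,980 ng/mL is about 3% of the 313,000 ng/mL peak, so later cycles should resemble the first. This softens the concern, but it rests on prediction, and cumulative effects unrelated to concentration stay unmeasured.
- **Section 1.3.2 does not promise every test.** PT/INR, aPTT, fibrinogen and D-dimer run to Day 113 and could satisfy its sentence. That reading is possible. However, ATIII is named one sentence before the commitment. Troponin is listed separately, so no conflict is claimed for it.
- **Other safeguards continue.** AEs, PF1+2, thrombin generation and dPT run to Day 113. Other Appendix 2 criteria can still be triggered, any thrombotic event suspends dosing, and escalation decisions need data through Day 29 at a minimum. This explains dense early testing. It does not justify a Day 113 label.
- **SAP 6.5.4 reports ECG by study day.** Readers could see where scheduled ECGs end, but the maximum-value tables carry no such marker.

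**Conclusion.** The concern holds. Three named components of the primary safety endpoints have a window to Day 113 and a schedule that ends before the Day 29 dose. The gap is 84 of 112 days, 8 of 12 SC doses and 2 of 3 IV doses, with no scheduled IV repeat-dose result for any of the three. It concerns scheduled collection of these measures, not thrombosis monitoring as a whole, and no formal safety test depends on it. It should be fixed because the endpoint as written cannot be delivered on schedule and two of the measures are treatment-stopping criteria.

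The conclusion assumes nominal visit days and takes the pre-dose timing at Day 29 from the order of procedures in 6.2.3. The ATIII conflict with 1.3.2 also assumes that the commitment there covers the parameters just listed.

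**What to change.** 1. **ATIII:** report it at Days 57, 85, 113 and early withdrawal from the combined coagulation tube. Add it to Table 2 and to Sections 6.2.6, 6.2.8, 6.3.1 and 6.4, and amend footnote b of Tables 6 and 7. Cost: assay fees only.
2. **Troponin I (preferred, not essential):** add a 3 mL sample at the same visits, amend footnote d and update the Section 7.7 totals. Cost: up to 9 mL and three assays per subject; a withdrawal draw replaces the visits then missed. Section 7.7 says the total should not rise but goes on: "Additional blood samples may be taken for safety assessments at times specified by Pfizer".
3. **Any measure not extended, ECG included:** restate its window as Day 1 to Day 29 in Protocol 2.2.1 and SAP 3.1. Label the SAP 6.5.4 maximum ECG tables with the days actually covered. If ATIII is not extended, correct Section 1.3.2 too.

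No new visits are needed. Even the text-only option needs a protocol amendment with IRB/EC approval at about 20 sites, so it is best combined with the next amendment.

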### 2.2.2. Secondary Endpoints

- Efficacy:
  - Frequency and annualized rate of bleeding episodes; Day 1 up to Day 85.
- Pharmacokinetics:
  - Plasma PF-06741086 concentrations (Day 1 up to Day 113) and noncompartmental parameters will be calculated as determined by a validated assay:
    - Single-dose.
    - Day 1 to Day 7 (QW):  $C_{max}$ ,  $T_{max}$ ,  $AUC_{last}$ ,  $C_{168h}$ .
    - Day 1 to Day 28 (QM):  $C_{max}$ ,  $T_{max}$ ,  $AUC_{last}$ ,  $C_{672h}$ .
    - Multiple-dose Day 29 to Day 36 (QW) or Day 29 to Day 57 (QM)  $C_{max,ss}$ ,  $T_{max,ss}$ ,  $AUC_{\tau}$ ,  $V_{ss}$  (for IV administration only), CL (for IV administration only) or CL/F (for SC administration only), and  $C_{min}$ .
- Pharmacodynamics:
  - Total TFPI; Day 1 up to Day 113.

- Thrombin generation (including lag time, peak thrombin generation and endogenous thrombin generation potential); Day 1 up to Day 113.
- Prothrombin fragment 1+2; Day 1 up to Day 113.
- D-dimer; Day 1 up to Day 113.
- Dilute prothrombin time; Day 1 up to Day 113.
- Immunogenicity:
  - Frequency of anti-drug antibody (ADA) and neutralizing antibody (NAb) production against PF-06741086; Day 1 up to Day 113. Only positive ADA samples and the corresponding baseline sample will be tested in the NAb assay.

CCI

[figure not shown]
### 3. STUDY DESIGN

B7841002 will be an open-label investigation of the safety, tolerability, PK, PD, and efficacy of multiple SC or IV doses of PF-06741086 in males with hemophilia A or B, with or without inhibitors to FVIII or FIX. The subjects, investigator, site personnel, and Sponsor will not be blinded to the treatment assignment.

Subjects with severe hemophilia A or B (defined by factor VIII or factor IX activity  $\leq 1\%$ ), including subjects with inhibitors to factor VIII or factor IX (positive inhibitor test result [above the upper limit of normal]), who receive bypass agents as primary treatment for bleeding episodes) will be recruited into B7841002. Subjects with inhibitors who are currently treated with activated prothrombin complex concentrate (APCC, eg, FEIBA) and cannot substitute treatment with recombinant factor VIIa (rFVIIa, eptacog alfa [activated]) as their standard of care for treatment of acute bleeding episodes (at a dose level of approximately 90  $\mu\text{g}/\text{kg}$ ) for the duration of the study are not eligible. Subjects must be on an episodic (on-demand) treatment regimen at the time of study enrollment and also have a documented history of at least 6 acute bleeding episodes in the 6 months prior to study enrollment. Subjects must washout from any factor replacement or *bypass* agent therapy prior to screening and prior to study treatment.

The following schematic is meant to demonstrate the planned dose progression scenario:

**Figure 1. Dose Progression Scheme**

SC or IV multiple dose cohorts will be enrolled starting at the 300 mg SC dose. Subjects will be enrolled and assigned to treatment as follows.

- Cohort 1 (n=6): 300 mg PF-06741086 SC QW (n=6).
- Cohort 2 (n=6): 300 mg SC loading dose, 150 mg PF-06741086 SC QW (n=6).
- Cohort 3 (n=6): 450 mg PF-06741086 SC QW (n=6).
- Cohort 4 (n=6): 1000 mg PF-06741086 IV QM (n=6).

Doses, frequency and route(s) of administration after the first dose may be modified based on review of available data. Additional subjects or cohorts may be added for reasons described in [Section 3.1](#).

Safety endpoints will include TEAEs (graded by the NIAID DMID severity scale), infusion/injection site reactions, laboratory parameters that may be modulated due to coagulopathy (eg, PT/INR, activated aPTT, fibrinogen, ATIII, platelet counts) and parameters to screen for possible thrombotic events (eg, cardiac troponin I). PK and PD endpoints include concentrations of PF-06741086 in plasma, non-compartmental PK parameters, measures of target binding by PF-06741086 (ie, TFPI level) or downstream pharmacological activities of TFPI inhibition (ie, dPT, thrombin generation, PF1+2, and D-dimer).

### **3.1. Planned Number of Subjects**

Approximately 24 subjects are planned for enrollment at approximately 20 study sites. Subjects who are withdrawn for reasons other than safety may be replaced at the discretion of the Sponsor. Subjects with inhibitors to FVIII or FIX will only be enrolled into a cohort with a dose level and regimen that was previously assessed as safe and well tolerated in subjects without inhibitors. Additional subjects and/or cohorts may be enrolled in the event that the number of dosing cohorts or size of dosing cohorts is increased to fully define the dose range and/or clinical profile at the respective dose levels.

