Subjects who meet the eligibility criteria will be assigned to a PF-06741086 treatment cohort, defined by a specific dose level, dose frequency and route of administration. Subjects will be treated with PF-06741086 for up to 3 months, with a maximum of 5 months expected for overall study participation. Approximately 24 subjects (4 treatment cohorts with 6 subjects per cohort) are planned to be treated. The planned number of subjects, cohorts, dose levels, dose frequencies and route of administration may change depending on the results from each cohort dosed in the study.

Subjects will be required to attend weekly clinic visits during the first month of the study (Day 1 to Day 29). An additional two clinic visits at Day 2 and Day 4 will be required for PK/PD blood draws. Through Day 29 (at a minimum), data will be reviewed to determine if PF-06741086 is safe and well tolerated. Dosing of subjects in any cohort may be stopped if the B7841002 protocol-specified stopping criteria are met, or if available data indicate that the current dose is not safe and well tolerated. If available safety, tolerability and PK data through Day 29 are permissive for dose escalation, a cohort at a higher dose level (SC or IV administration) may be opened for enrollment. Alternatively, a cohort at a lower dose level may be opened if data are supportive.

In addition, if the dose level under review is safe and well tolerated through Day 29, treatment will continue for the subjects in that respective cohort during the subsequent 2 months (Day 30 to Day 85). During this period, clinic visits at Day 30 and Day 33 will be required for PK/PD blood draws for all cohorts. Subjects in the SC cohorts will receive treatment on Day 36, Day 43, Day 50, Day 57, Day 64, Day 71, Day 78, follow-up on Day 85, and end-of-study procedures on Day 113. Subjects in the IV cohort will return to the clinic for treatment on Day 57, follow-up on Day 85, and end-of-study procedures on Day 113. Follow-up beyond Day 113 may be required for any subjects that test positive for an anti-drug or neutralizing antibody during the study.

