### **9.1. Sample Size Determination**

The total sample size of approximately 24 subjects for 4 dose cohorts is based on clinical considerations to provide adequate safety, tolerability, PK, PD and efficacy information at each dose level and/or route of administration. Each single dose cohort includes 6 subjects to ensure sufficient sample size for assessment of safety, PK, PD and efficacy. Additional subjects and/or cohorts may be added to fully explore the dose range and efficacy.

This sample size is also considered sufficient to support initial analyses for efficacy based on the endpoint of annualized bleeding rate (ABR). With 6 subjects per cohort, there is greater than 80% power to detect an 85% reduction in ABR compared to a historical factor-replacement treatment (control group) at one-sided alpha of 0.1. The power calculation is based on a Poisson regression model with assumptions that the historical control group has a bleeding rate of 2.36/patient-month and the study duration is 3 months.

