2.2. Study Design

B7841002 will be an open-label investigation of the safety, tolerability, PK, PD, and efficacy of multiple SC or IV doses of PF-06741086 in males with severe hemophilia A or B. The subjects, investigator, site personnel, and Sponsor will not be blinded to the treatment assignment.

The following schematic is meant to demonstrate the planned dose escalation scenario:

Figure 1. Dose Escalation Scheme

SC/IV multiple dose cohorts will be enrolled in a dose-escalating fashion starting at the 300 mg SC dose. Subjects will be enrolled and assigned to treatment as follows:

- Cohort 1 (n=6): 300 mg PF-06741086 SC QW (n=6);
- Cohort 2 (n=6): 300 mg SC loading dose, 150 mg PF-06741086 SC QW (n=6);
- Cohort 3 (n=6): 450 mg PF-06741086 SC QW (n=6);
- Cohort 4 (n=6): 1000 mg PF-06741086 IV QM (n=6).

Doses, frequency and route(s) of administration after the first dose may be modified based on review of available data. Additional cohorts may be added for reasons described in protocol Section 3.1.

Approximately 24 subjects are planned for enrollment at up to approximately 20 study sites. Subjects who are withdrawn for reasons other than safety may be replaced at the discretion of the Sponsor. Subjects with inhibitors to FVIII or FIX will be enrolled into cohorts currently open for enrollment. Additional subjects and/or cohorts may be enrolled in the event that the number of dosing cohorts or size of dosing cohorts is increased to fully define the dose range and/or clinical profile at the respective dose levels.

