5.2.3. Analyses for Count Data

Separate models will be run for each pairwise comparison between the historical control group and each dose cohort. The frequency of bleedings will be analyzed using a negative binomial model. Log transformed duration of time on study will be included as an offset variable in the model.

Sample SAS codes are provided as follows:

```
PROC GENMOND Data=sample;
  Where dose='300mg SC';
  Class trt;
  Model count=trt/dist=negbin link=log offset=logtime alpha=0.2 ;
  Estimate 'PF-06741086 - PCB' trt 1 -1;
  Estimate 'PF-06741086' intercept 1 trt 1/alpha=0.2;
  ods output ParameterEstimates=pvalue estimates=est;
```

Run;

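### Protocol 3.1 and SAP 2.2 give different enrolment rules for inhibitor subjects, and the SAP's bleeding-rate comparison sets any who enrol against a factor-treated control that is not their comparator

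*Protocol*

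**What the plan says.** **Objective and size.** Protocol 2.1 concerns safety and tolerability of multiple doses "administered to severe hemophilia A and B subjects with and without inhibitors against FVIII and FIX". The Protocol Summary states: "Approximately 24 subjects (4 treatment cohorts with 6 subjects per cohort) are planned to be treated". The list under Protocol Figure 1 gives each cohort its own regimen, starting with "Cohort 1 (n=6): 300 mg PF-06741086 SC QW (n=6"). The others are 150 mg SC weekly after a 300 mg loading dose, 450 mg SC weekly, and 1000 mg IV monthly.

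**Enrolment of inhibitor subjects.** Protocol 3.1 says they "will only be enrolled into a cohort with a dose level and regimen that was previously assessed as safe and well tolerated"; the assessment it refers to is one made in non-inhibitor subjects. SAP 2.2 says: "Subjects with inhibitors to FVIII or FIX will be enrolled into cohorts currently open for enrollment". The SAP states that it is based on protocol amendment 4.

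**Efficacy comparison.** Protocol 9.1 bases power on an 85% reduction "compared to a historical factor-replacement treatment (control group"). SAP 6.2.1.1 builds the control from on-demand data in one ReFacto AF and two BeneFIX studies, filtered on age and factor activity. SAP 5.2.3 runs one negative binomial model per dose cohort against that control. Treatment is the only model term, and the sample code selects rows with "Where dose='300mg SC"'. SAP 5.1 declares superiority if the upper 80% limit of the ratio is below 1 and the estimate is at most 0.3, testing cohorts in order of exposure.

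**Inhibitor subjects in the analysis.** Inclusion criterion 5 requires a bypass agent as their primary bleed treatment. Protocol 9.2.1 plans ABR by inhibitor status, overall and by dose level. SAP 6.2.1.2 has subgroups by hemophilia A and B only.

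**The concern.** There are three linked problems.

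1. The two documents differ on who may enter a regimen being tested for the first time. Protocol 3.3 counts dose-limiting toxicities in a cohort of 6 and reviews all 6 through Day 29 before moving to a new higher dose or regimen. Which rule is followed affects whether an inhibitor subject may be one of those 6.
2. The objective covers inhibitor subjects, but no document says how many are expected or in which cohort.
3. Once inhibitor subjects are treated, the only efficacy comparison in the SAP sets them against patients whose bleeds were managed with factor products. Protocol 1.3.4 describes the reference as the bleeding history of patients on factor replacement or on bypass therapy. The SAP names no bypass-treated source.

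At stake is the superiority decision in SAP 5.1. For any dose with inhibitor subjects, the ratio would combine the drug effect with whatever difference exists between the two on-demand populations. Because testing is hierarchical, a shifted result in one cohort also decides whether lower-exposure cohorts are tested at all.

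**Working it through.** **1. The plan's own figures.** 4 cohorts × 6 = 24, as stated. For power, the control mean is 2.36 × 3 = 7.08 bleeds per subject, and 7.08 × 0.15 = 1.062 on treatment. A Poisson Wald test on the log ratio has variance 1/(6 × 1.062) + 1/(n_c × 7.08). The control size n_c is not given. With n_c = 6 the variance is 0.157 + 0.024 = 0.180, so z = 1.897/0.425 − 1.282 = 3.18 and power is 99.9%. A larger control gives slightly more. The stated power above 80% is correct as a lower bound, and sample size is not the difficulty here.

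**2. Places for inhibitor subjects.**

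| Rule | Inhibitor places within the nominal 24 |
|---|---|
| Protocol 3.1, if each regimen's first 6 must be assessed first | 4 × (6 − 6) = 0 |
| SAP 2.2 as written | 0 to 24 |

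One repeat cohort of 6 would bring the total to 24 + 6 = 30. The zero depends on carrying the 6-of-6 review in Protocol 3.3 over to inhibitor admission, which Protocol 3.1 does not say.

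**3. The comparator, side by side.**

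| | Inhibitor subject in the trial | Historical control |
|---|---|---|
| Bleed treatment | Bypass agent (criterion 5) | Factor replacement (Protocol 9.1; ReFacto AF and BeneFIX studies, SAP 6.2.1.1) |
| Selection on inhibitor status | Positive test required | No filter stated |
| Term in the model | None | None |

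If inhibitor subjects share a dose cohort with others, they enter that cohort's ratio. If they form their own cohort, the whole ratio is against the factor-treated control. The mismatch exists in both cases.

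**4. Illustration of size.** Let r be the inhibitor to non-inhibitor on-demand bleeding rate and m the number of inhibitor subjects among 6. Neither is in the documents; r = 0.5 to 2 is an assumption. With the same drug effect in both groups, the expected ratio is 0.15 × [1 + (m/6)(r − 1)].

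| m | r = 0.5 | r = 1 | r = 2 |
|---|---|---|---|
| 2 | 0.125 | 0.15 | 0.20 |
| 3 | 0.1125 | 0.15 | 0.225 |
| 6 | 0.075 | 0.15 | 0.30 |

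In a Poisson simulation with an assumed control of 50, the chance that the estimate is at most 0.3 is 98.7% with no inhibitor subjects. With r = 2 it is 91.7% (m = 2), 84.4% (m = 3) and 51.6% (m = 6). With r = 0.5 it is at least 99.7% for the same values of m.

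**5. Reporting.** Safety by inhibitor status is covered: Protocol 9.6 plans abnormal findings separately, and SAP 6.5.1 plans adverse events by inhibitor status. ABR by inhibitor status is in Protocol 9.2.1 but in no SAP output.

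**The case against.** The best defence is that the plan is flexible. The number is approximate. The Protocol Summary and Section 3.1 allow cohorts to be added, enlarged or changed, and 3.1 allows replacement of subjects withdrawn for non-safety reasons. Section 3.1 does not say how many non-inhibitor subjects must be assessed first. An open cohort can also be one at a regimen already assessed, so both enrolment sentences can hold at once. The objective is descriptive, with no formal hypothesis.

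Most of this stands, and it rules out several stronger readings:

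- **That none of the 24 can have an inhibitor, or that the trial cannot address inhibitor subjects.** The documents provide routes for enrolling them and plan safety summaries for them. What is missing is any statement of which route will be used.
- **That SAP 2.2 says the opposite of Protocol 3.1.** It omits the restriction; it does not deny it.
- **That inhibitor subjects will certainly be pooled with others.** The text of SAP 5.2.3 works by dose cohort, and the selection by dose appears only in sample code. Pooling is possible but not established.
- **That the mix pushes a result across the 0.3 cut.** With 2 of 6 and r = 0.7 to 1.5, the factor (4 + 2r)/6 runs from 0.90 to 1.17. A true ratio of 0.30 would read 0.27 to 0.35, but only because it starts on the cut. At the design ratio of 0.15 the same factor gives 0.135 to 0.175.

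The flexibility does not answer the comparator problem. No route for enrolling inhibitor subjects gives them a bypass-treated reference, and SAP 5.1 makes no exception for them.

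**Conclusion.** The concern holds in three parts.

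- **Enrolment.** Protocol 3.1 and SAP 2.2 differ and must be reconciled. No view is taken here on which rule should stand. Under the Protocol rule the nominal 24 appear to reserve no inhibitor places unless a cohort is added, repeated or expanded. That is an inference from four distinct regimens of 6, not a stated exclusion.
- **Comparator.** The historical ratio and the SAP 5.1 decision are not suited to inhibitor subjects, whether they share a cohort or form one. The documents give no inhibitor bleeding rate and do not say whether the control studies included inhibitor patients, so the size and direction of the bias are unknown. The range of 0.125 to 0.20 for 2 of 6 rests on the assumed r, an equal drug effect, and the design ratio of 0.15.
- **Reporting.** SAP 6.2.1.2 leaves out an ABR summary that Protocol 9.2.1 requires. This needs no assumption.

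The change should be made before the analysis. It does not call the primary safety objective or the stated power into question.

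**What to change.** (a) Reconcile SAP 2.2 with Protocol 3.1. Once one rule stands, state where the inhibitor data will come from.

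(b) In SAP 5.1, 5.2.3 and 6.2.1.1, run the historical ratio and the superiority decision in non-inhibitor subjects only, and show the all-subject ratio as a sensitivity result. The Wilcoxon test in SAP 6.2.1.3 uses the same control and hierarchy and should follow suit.

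(c) In SAP 6.2.1.1 and 6.2.1.2, report ABR by inhibitor status, overall and by dose level. Where data permit, give inhibitor subjects a model-based ABR with its 80% CI, and no ratio to the factor-treated control.

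**Cost.** The change needs SAP wording, one extra selection condition in the model, and a protocol clarification if the reconciled rule requires it. The downside is fewer subjects in the decision at any dose that includes inhibitor subjects. If 3 of 6 remained, the test of the ratio against 1 with a control of 6 would have variance 1/(3 × 1.062) + 1/(6 × 7.08) = 0.337, giving power of 97.6% against 99.9% with all 6. With an assumed negative binomial dispersion of 1, the variance becomes (1/1.062 + 1)/3 + (1/7.08 + 1)/6 = 0.837, and power is 78.6% against 91.4%. With a control of 50 and that dispersion it is 85.0% against 97.4%. So the loss is small without overdispersion and noticeable with it.
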